6.2 Toxicity

6.2.1. Definition of Dose-Limiting Toxicity

DLT will be defined employing the National Cancer Institute Common Terminology Criteria for Adverse Events, Version 5.0 (CTCAE v5.0), except IRR/CRS which will be defined by the modified criteria proposed by ASCT and described in section 4.7.1 and in Table 4.

DLT is defined as:

- Grade 4 neutropenia lasting \geq 42 days from start of cycle in absence of evidence of active AML (< 5% blasts).
- The development of acute or chronic graft-versus-host disease during treatment
- Grade 3–5 nonhematologic toxicity that is possibly, probably or definitely related to the study drug

EXCEPT:

- Grade 3 fatigue, asthenia, fever, anorexia, or constipation
- Grade 3 nausea, vomiting or diarrhea not requiring tube feeding, total parenteral nutrition, or requiring or prolonging hospitalization;
- Infection, bleeding, or other expected direct complication of cytopenias due to active underlying disease;
- Grade 3 or 4 tumor lysis syndrome (TLS) or disseminated intravascular coagulopathy (DIC) if it is successfully managed clinically and resolves within 7 days without end-organ damage;
- Grade 3 or 4 isolated electrolyte abnormalities (i.e., those occurring without clinical consequence) that resolve, with or without intervention, to Grade 2 levels in < 72 hours will not be considered DLT.
- Grade 3 CRS/IRR that is successfully managed and resolves within 72 hours, as this is an expected event that does not require permanent treatment discontinuation
- Any non-leukemia-related death occurring within 90 days of treatment initiation

Treatment discontinuation for adverse events prior to the completion of one cycle will be considered a DLT unless the adverse event is disease progression, which necessitates alternative therapy, or the adverse event is not possibly, probably, or definitely due to the study treatment. Patients who discontinue treatment prior to the completion of one cycle for progressive disease or due to an event that is not possibly, probably, or definitely due to the study treatment will be replaced.

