8.2. Study Design

This study proposal will be a phase 1 trial of flotetuzumab in patients with relapsed/refractory AML following alloHSCT. The first part of the study will be a dose escalation following a 3+3 design for post-transplant flotetuzumab. The study will start with the recommended dose of flotetuzumab in relapsed/refractory ALL (DL1). The first three patients will be enrolled and monitored for the first cycle of treatment for DLTs through the full DLT period (90 days) before enrolling additional patients. If less than 2 patients experience a DLT, an additional 3 patients will be enrolled. If 0 or 1 out of 6 patients have a DLT, then the dose will be deemed safe and considered the MTD of flotetuzumab in the post-transplant setting. If 2 or more of the first 3 or 6 patients experience a DLT, then the trial will proceed to enroll patients at DL-1 starting with 3 patients. The first three patients on DL-1 will be enrolled and monitored in the first cycle of treatment for DLTs through the full DLT period (90 days) before enrolling additional patients. If less than 2 patients experience a DLT at DL-1, an additional 3 patients will be enrolled at DL-1. If 0 or 1 out of 6 patients have a DLT at DL-1, then the dose will be deemed safe and the MTD. If 2 or more of the first 3 or 6 patients experience a DLT, then the trial will be stopped. An expansion cohort of 4 subjects will be also pursued at MTD for flotetuzumab to further characterize safety, tolerability and any preliminary signs of biological or clinical activity in this cohort. DLT monitoring will continue in this expansion cohort, and the trial will be stopped if two additional subjects experience a DLT. Any patient who discontinues treatment prior to the completion of one cycle of flotetuzumab for disease progression or for an adverse event that is not possibly, probably, or definitely due to the study treatment will be replaced.

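### The 90-day non-leukemia death item in 6.2.1 does not fit the rest of the DLT rule, whether read as an exception or as a criterion, and no text says whether a replaced patient's DLT counts

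*Combined protocol and SAP*

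**What the plan says.** Section 6.2.1 gives three DLT criteria. One is Grade 3–5 "nonhematologic toxicity that is possibly, probably or definitely related to the study drug". A list headed EXCEPT follows, and its last bullet is "Any non-leukemia-related death occurring within 90 days of treatment initiation". That bullet carries no relatedness condition.

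The next paragraph of 6.2.1 makes stopping treatment for an adverse event before the end of cycle 1 a DLT, "unless the adverse event is disease progression, which necessitates alternative therapy", or unless the event is unrelated to study treatment. It then provides for replacement of two groups. The first is "Patients who discontinue treatment prior to the completion of one cycle for progressive disease". The second is those who stop equally early because of something unrelated to flotetuzumab.

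Section 8.2 repeats the replacement rule ("Any patient who discontinues treatment prior to the completion of one cycle of flotetuzumab for disease progression", or for an unrelated adverse event). It has the first three patients at each dose level monitored "for DLTs through the full DLT period (90 days) before enrolling additional patients". The decision rule at DL1 is: "If 0 or 1 out of 6 patients have a DLT, then the dose will be deemed safe" and becomes the MTD. Two or more DLTs in the first 3 or 6 send the trial to DL-1, and the same count at DL-1 stops it. The 4-patient expansion stops on two additional DLTs.

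Neither section mentions the death item and the replacement rule together.

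**The concern.** The MTD is a primary endpoint (8.1.1) and rests on a count of 0–1 versus 2 or more DLTs in six patients. A rule that turns on one patient needs a defined numerator and denominator. Here, whether the death item is a DLT criterion or an exemption depends on where a bullet belongs. If it is a criterion, some patients meet both it and the replacement rule, and no order of precedence is given. If this stays open, the choice would be made after a death has occurred, when its effect on the dose decision is already known.

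**Working it through.** **Step 1: the two readings.** They are alternatives and cannot both hold.

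- *Exception, as printed.* A non-leukemia death by day 90 is exempt from the Grade 3–5 criterion. Replacing a patient with an unrelated death then conflicts with nothing. But a drug-related nonhematologic death is also exempt, although Grade 5 is named in that criterion. Because 8.2 sets the DLT period at the same 90 days, Grade 5 would have no effect through that criterion during the period.
- *Separate criterion.* A non-leukemia death by day 90 is a DLT whatever its cause. The clause beginning with unless removes only discontinuation as a route to a DLT; it does not cancel another criterion. Three kinds of patient are then a DLT and also to be replaced: (a) one who dies in cycle 1 of an unrelated non-leukemia cause, if death counts as discontinuation; (b) one taken off in cycle 1 for an unrelated event who dies of a non-leukemia cause by day 90; (c) one taken off in cycle 1 for progression who dies of a non-leukemia cause by day 90.

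Case (c) can arise from the plan's own text. Section 6.2.1 expects alternative therapy after progression, 4.10 places other cytotoxic chemotherapy and donor lymphocyte infusion after study treatment ends, and 4.12 follows patients for death for two years.

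**Step 2: effect of one patient.** Take six patients with one other DLT and one patient of type (a)–(c). Counted: 1 + 1 = 2 of 6, so the trial leaves DL1 (or stops, if at DL-1). Replaced by a patient without a DLT: 1 of 6, so the dose is the MTD.

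**Step 3: how often the readings differ.** The documents give no rates for this population, so both inputs are assumptions:

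- q = proportion with any other DLT, 10%
- d = proportion of type (a)–(c), 1%, 2% or 5%, taken as not overlapping with q

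Patients who stop for progression and have no non-leukemia death by day 90 are replaced either way and are left out.

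Counted: p = q + d. Replaced and not counted: p = q/(1 − d). The dose passes with probability P(X ≤ 1) = (1 − p)^6 + 6p(1 − p)^5.

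For d = 5%:
- counted, p = 0.15: 0.377 + 0.399 = 0.776
- replaced, p = 0.10/0.95 = 0.1053: 0.513 + 0.362 = 0.875
- difference 0.099

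| d (assumed) | Pass if counted | Pass if replaced | Difference |
|---|---|---|---|
| 1% | 0.866 | 0.884 | 0.018 |
| 2% | 0.844 | 0.882 | 0.037 |
| 5% | 0.776 | 0.875 | 0.099 |

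(Differences are taken before rounding.) A trial that passes when these patients are counted also passes when they are replaced: if the only DLT is such a patient, the other five have none and the substitute adds at most one. The difference is therefore the share of trials with opposite decisions. If the two events are instead independent (counted p = 1 − (1 − q)(1 − d), replaced p = q), the differences are 0.018, 0.037 and 0.098. With q = 20% and no overlap they are 0.020, 0.039 and 0.096.

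**Step 4: expansion.** P(2 or more DLTs in 4) at q = 10%, no overlap, is 0.062, 0.073 or 0.110 if counted, against 0.053, 0.054 or 0.058 if replaced.

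**Step 5: sample size.** The plan's own figures reproduce: 6 + 6 + 4 = 16 at most, and 6 + 4 = 10 at one dose level. Neither includes replaced patients.

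**The case against.** The strongest reply is that replacement is nowhere said to mean not counted. If the death item is a criterion, 8.2 counts patients who experience a DLT, nothing removes a DLT already met, and the natural reading is that it counts. On that view a clarifying sentence is missing and no two rules contradict each other. This stands in part. A reader might infer a flat contradiction between 6.2.1 and 8.2, and the text does not support that. But if such a patient is both counted and replaced, seven patients stand behind a rule written for six, and the plan does not say how to apply it. The calculation compares counted with replaced and not counted; it does not model counted and also replaced.

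A reader might also infer that the protocol deliberately exempts fatal drug toxicity. The documents do not support that either: lost indentation in the PDF text could have moved an outer-level bullet into the exception list.

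The cases are also narrow. Death is not among the twelve reasons for ending treatment in 4.11, so (a) is uncertain. Case (c) needs a death judged not leukemia-related in a patient with progressing AML. A drug-related nonhematologic death in (c) already meets the Grade 3–5 criterion if the bullet is not an exception. Under any reading, deaths are reported as serious adverse events (9.4), and 9.6 allows the trial to be put on hold. These provisions limit the safety consequence but do not define the DLT count.

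**Conclusion.** The point holds as an inconsistency that should be fixed. Neither reading of the death item gives a consistent rule for the 0–1 versus 2-or-more decision. Either a fatal related toxicity is exempted against the Grade 3–5 criterion, or some patients are both a DLT and replaced with no statement of whether they count. One such patient can decide the MTD.

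The likely size is modest: about 2%, 4% or 10% of trials if 1%, 2% or 5% of patients are affected, with other DLTs at 10%. All these rates are assumed. At d = 10% the same formulas give 0.655 against 0.863, about 21%. A reader might take that as the expected size, but no figure in the documents supports such a rate. The direction is the same throughout: counting makes it less likely that the dose passes. No stated sample size is wrong because of this point.

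**What to change.** Reconcile 6.2.1 and 8.2 before enrolment:

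- Place the death item unambiguously among the DLT criteria or among the exceptions, consistently with the Grade 3–5 criterion.
- State in both sections whether a patient who meets a DLT criterion by day 90 after leaving treatment in cycle 1 stays in the numerator and denominator (of the 3, the 6 and the expansion) or is replaced and not counted.
- State whether death in cycle 1 counts as discontinuation.

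Which rule applies is for the sponsor and investigator to decide.

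The cost is a few sentences. Each choice has a downside. Counting lets an unrelated death, including one after later therapy, weigh against the dose. Replacing adds patients: they fit within the maximum of 16 in 8.3.1 if only DL1 and the expansion are used (10 plus up to 6 replacements), but if both levels and the expansion fill, every replacement exceeds it.

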4.7.4. Other Clinically Relevant Adverse Events

If a grade 3 non-hematological adverse event occurs that is deemed by the investigator to be possibly, probably or definitely related to the study drug, then flotetuzumab will be withheld until the toxicity resolves to no more than grade 1 (mild) after which flotetuzumab may be restarted at the previously tolerated dose. If the toxicity persists for more than 14 days, then flotetuzumab will be permanently discontinued. If a grade 4 non-hematological adverse event occurs that is deemed by the investigator to be possibly, probably or definitely related to the study drug, then flotetuzumab should be permanently discontinued.

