9.3. Adverse Event Definition

An adverse event is any untoward medical occurrence in a clinical study subject administered a medicinal (investigational or non-investigational) product. An adverse event does not necessarily have a causal relationship with the treatment. An adverse event can therefore be any unfavorable and unintended sign (including an abnormal finding), symptom, or disease temporally associated with the use of a medicinal (investigational or non- investigational) product, whether or not related to that medicinal (investigational or non-investigational) product. (Definition per International Conference on Harmonisation [ICH])

This includes any occurrence that is new in onset or increased in severity or frequency from the baseline condition, or abnormal results of diagnostic procedures, including laboratory test abnormalities (except Grade 1 and 2 hematologic and metabolic abnormalities) that are deemed clinically significant by the principal investigator.

This study will utilize the Common Terminology Criteria for Adverse Events (CTCAE) version 5.0 for adverse event reporting, except for IRR/CRS, which has been defined in Table 4. In cases where CTCAE version 5.0 cannot be applied to the toxic event, the investigator will quantify the toxicity based on the intensity as defined:

1. Mild: The subject is aware of the signs or symptoms but they are easily tolerated; usually does not require additional therapy or discontinuation of study drugs.
2. Moderate: The signs and symptoms are sufficient to restrict but do not prevent usual activity; possibly requires additional therapy but usually does not require discontinuation of the study drug.
3. Severe: The subject is unable to perform usual activities and usually requires discontinuation of the study drug.

Patients are to be followed for adverse events for 30 days after the last dose of the study drug and any adverse event occurring in a patient up to 30 days after stopping the study drug or until the start of a subsequent systemic anticancer therapy, if earlier, must be reported. The surveillance period after study drug discontinuation may be extended if there is a strong

suspicion that the drug has not yet been eliminated or if the nature of a particular event may suggest long-term effects from the investigational drug, as assessed by the investigator.

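### Is DLT status left undefined when flotetuzumab is stopped in cycle 1 for a Grade 4 electrolyte abnormality that section 6.2.1 exempts?

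*Combined protocol and SAP*

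**What the plan says.** Section 6.2.1 lists the DLT criteria. One is a Grade 3 to 5 nonhematologic toxicity at least possibly related to the drug, and a list of exceptions follows it. One exception is "Grade 3 or 4 isolated electrolyte abnormalities (i.e., those occurring without clinical consequence) that resolve, with or without intervention" to Grade 2; that bullet ends "72 hours will not be considered DLT". Another exempts Grade 3 cytokine release or infusion reactions (CRS/IRR) that are managed and resolve within 72 hours, "as this is an expected event that does not require permanent treatment discontinuation".

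After the list comes a separate paragraph: "Treatment discontinuation for adverse events prior to the completion of one cycle will be considered a DLT unless the adverse event is disease progression", or unless the event is unrelated to treatment. Patients who stop before completing one cycle for either of those two reasons are replaced.

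Section 4.7.4 governs management. "If a grade 4 non-hematological adverse event occurs that is deemed by the investigator to be possibly, probably or definitely related" to the drug, "then flotetuzumab should be permanently discontinued". It has no carve-out for electrolyte abnormalities. Related Grade 3 events lead to withholding, with restart allowed.

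Section 9.3 treats laboratory abnormalities above Grade 2 as adverse events when they are ones "that are deemed clinically significant by the principal investigator".

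Section 8.2 deems a dose safe, and the MTD, at 0 or 1 DLT in 6 patients. Two or more lead from DL1 to DL-1, or stop the trial at DL-1. Two additional DLTs stop the trial during expansion.

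**The concern.** Take a patient in cycle 1 with a related, isolated Grade 4 electrolyte abnormality that is back to Grade 2 within two days. The exception list says this is not a DLT. If the investigator follows 4.7.4 and stops the drug, the closing paragraph of 6.2.1 says it is one, because its carve-outs cover only progression and unrelated events. No sentence in 6.2.1, 4.7.4 or 8.2 says which provision prevails.

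The MTD is a primary endpoint (section 8.1.1) and rests on six patients, so a single classification can move a dose level from safe to not safe. If the rule were truly open, it might be settled only after the patient had been seen.

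**Working it through.** The plan gives no operating characteristics for the DLT rule, so there is no stated figure to reproduce. The check is textual first, then a sizing of the consequence.

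**1. What each provision governs.** The exception list hangs on the nonhematologic-toxicity bullet and decides whether the event itself is a DLT. The closing paragraph has a different trigger, discontinuation before the end of cycle 1, and its own exceptions. A rule with its own exceptions does not inherit those of another criterion. Read this way the provisions do not collide: the transient abnormality alone is not a DLT, but a related discontinuation in cycle 1 is.

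**2. Consistency with the rest of 6.2.1.** The replacement rule matches the closing paragraph's two carve-outs exactly. If the exception list overrode the closing paragraph, a patient stopped early for a related exempt event would be neither a DLT nor replaceable, leaving a hole in the 3+3 count. The CRS/IRR exception is justified by the absence of any need to stop permanently, which fits a scheme in which permanent stopping bears on DLT status.

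**3. What the exception still does.** It applies to Grade 3 abnormalities, to Grade 4 abnormalities when the drug is not stopped, and to Grade 4 abnormalities after cycle 1 but within the 90-day DLT period of section 8.2.

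**4. How narrow the overlap is.** The abnormality must be without clinical consequence (6.2.1) yet clinically significant enough to be an adverse event (9.3). It must also be related, Grade 4, in cycle 1, back to Grade 2 in under 72 hours, and followed by permanent discontinuation. Section 6.2.3 lists no related Grade 4 electrolyte event in 66 patients. The related Grade 3 electrolyte events listed are hypocalcemia and hypophosphatemia, 2/66 each.

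**5. Consequence if one such patient occurs.** Put the patient among the first three at a dose level, with no other DLT. The classification changes the decision only if exactly one of the other five has a DLT. With an assumed rate b (the documents give none), the probability is 5b(1−b)⁴:

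- b = 0.10: 5 × 0.10 × 0.90⁴ = 0.328
- b = 0.15: 5 × 0.15 × 0.85⁴ = 0.392
- b = 0.20: 5 × 0.20 × 0.80⁴ = 0.410
- b = 0.25: 5 × 0.25 × 0.75⁴ = 0.396

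The early stop at 2 of the first 3 does not alter these values.

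**6. Allowing for rarity.** For 0/66 the exact one-sided 95% upper bound is 1 − 0.05^(1/66) = 0.044. Let p be the DLT rate from all other causes and q the per-patient probability of the disputed event. Then p′ = p + (1−p)q, and the probability that a dose is deemed safe is (1−p′)⁶ + 6p′(1−p′)⁵.

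| p | q = 0 | q = 1% | q = 4.4% |
|---|---|---|---|
| 10% | 0.886 | 0.868 | 0.800 |
| 20% | 0.655 | 0.636 | 0.569 |
| 30% | 0.420 | 0.405 | 0.356 |

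The last column overstates the issue. The 4.4% is a confidence limit for any related Grade 4 electrolyte event, not for the subset meeting every condition in step 4. At q = 1%, itself an assumption, counting the event as a DLT lowers the probability by 0.015 to 0.02.

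**The case for a change.** The best case for a change is that the electrolyte bullet is worded without qualification, and the two-route reading is inferred rather than stated. On that reading the Grade 4 part of the exception is idle in cycle 1 whenever 4.7.4 is followed, which is odd drafting. Because 4.7.4 says *should*, two patients with the same abnormality could be counted differently according to whether the drug was stopped. One sentence would settle the matter before a patient makes it matter.

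Some of this stands. The relation between the list and the closing paragraph is unwritten, and the same question arises for exempt Grade 4 tumor lysis syndrome, so it is not peculiar to electrolytes. But idle in one circumstance is not contradictory, and the exception keeps the uses in step 3. Dependence on the decision to stop comes with any criterion that counts discontinuations, and here that criterion was chosen openly. The proposed sentence would ask the sponsor only to say whether such a stop counts; it identifies no wrong result and no better rule.

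**Conclusion.** The concern does not call for a change. Applied as written, 6.2.1 gives a definite answer for this patient: a related discontinuation in cycle 1 is a DLT, whatever the status of the abnormality taken alone. That answer is also the cautious one for dose finding, since it can only raise the DLT count.

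The stake in a single case is real: 1/6 against 2/6, with a 0.33 to 0.41 chance of altering the decision under the assumed rates. The case itself should be rare, with none listed among 66 phase I patients. Carrying that experience into the post-transplant setting is an assumption, because section 2.10 says the drug has not been studied specifically there.

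The conclusion rests on reading the exceptions as attached to the event-based criterion, which the layout of 6.2.1 and its replacement rule support. It takes no position on when flotetuzumab should be stopped. A cross-reference between 4.7.4 and 6.2.1 would be a courtesy to the reader if the protocol is amended for other reasons.

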6.2.2. Infusion-related Reaction

Infusion-related reaction including cytokine release syndrome (CRS), which may be life-threatening or fatal, occurred in 81% of patients receiving flotetuzumab. The majority of these reactions were mild to moderate in severity, whereas 8% of patients treated at the RP2D experienced at least one severe (Grade 3) event. None of these events have been life threatening or fatal. Infusion reactions may be clinically indistinguishable from manifestations of

CRS. This typically occurs during the initial 48 hours of the first infusion of flotetuzumab. Symptoms of infusion-related reactions including CRS may include chills, fever, headache, fatigue, flushing, nausea, bronchospasm, and hypotension. Patients should be closely monitored for signs or symptoms of these events. For all patients receiving inpatient flotetuzumab infusion, vital signs should be monitored according to the inpatient standard-of-care. Management of these events may require either temporary interruption or discontinuation of flotetuzumab as described in Section [4.5.1](#).

